COVER PAGE – STUDY PROTOCOL

Title: Cranial electrotherapy stimulation: Piloting a road to PTSD prevention in first responders

NCT number: NCT06203717

Document date: 08/15/2024

BUTLER HOSPITAL
INSTITUTIONAL REVIEW BOARD
PROTOCOL

Project**Title of Project:** Cranial electrotherapy stimulation: Piloting a road to PTSD prevention in first responders**Short Title of Project:** CES in firefighters**Principal Investigator (PI):** [REDACTED]**Other Investigator(s):** [REDACTED]**Revision History:**

Version Number	Version Date	Summary of Revisions
1.0	08/28/2023	First version submitted
	09/18/2023	First version approved
2.0	12/14/2023	
 1. Changed PI from [REDACTED]. 2. Added [REDACTED] as co-investigator to the study team. 3. Corrected error in ecological momentary assessment (EMA). 4. Added new advertisement material.
3.0	05/28/2024	
 1. Revised CNE Research Application to change Device Risk Level to "nonsignificant risk device" instead of "N/A". 2. Updated protocol to include XNAT – a password protected secure server – for transfer of MRI data from MRF to Butler. 3. Broadening of recruitment locations to include community locations (e.g. coffee shops).
4.0	8/15/24	
 1. Broadening of recruitment methods through social media marketing. 2. Update protocol to allow for texting for initial outreach to potential participants.

Description of Study**A. Specific Aims**

Aim 1: Test the feasibility and acceptability of Cranial electrotherapy stimulation (CES) in firefighter first responders.

Prediction: CES is feasible quantified as more than 75% of sessions completed, and acceptable quantified as less than 20% attrition in the sample, such that at least 16 out of 20 firefighters complete, for example, at least 15 out of 20 sessions over the course of four weeks.

Aim 2: Test the effects of CES on subjective homeostatic functioning in firefighter first responders.

Prediction: CES will reduce subjective fatigue and frequency and intensity of negative emotions (e.g., distressed, nervous) while increasing the experience of positive emotions (e.g., calm, inspired) assessed naturalistically in near real-time through ecological momentary assessments (EMA).

Aim 3: Test the effect of CES on objective homeostatic functioning in firefighter first responders.

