ensure participants understand all procedures as well as assess tolerability of the individually determined stimulation intensity prior to sending participants home with the Alpha-Stim AID CES device. The device manual, a quick set-up guide for ease of reference, as well as information on the determined intensity and a pen-and-paper tracking log will be provided to participants to be used during the four-weeks of at home administered CES. Throughout the four weeks of CES, participants will be asked to document the day, time, and duration of CES application using the provided tracking log. Participants will be instructed to only use the Alpha-Stim AID CES device on 'off-duty days' (i.e., days on which they are not working). This is done as an extra precaution to avoid potential negative effects of CES on work-related performance as using heavy machinery immediately following CES is not advised per device manufacturer. The research team will check in with the participant at least once per week (or more often if indicated based on incomplete EMA surveys or difficulties using the CES device), during the four weeks of CES, starting on the second day after starting CES. This check-in will allow obtaining feedback on user feasibility as well as allow assessment for the presence of side effects/adverse events. We will use a recently adapted Side Effects Questionnaire based on the one developed by Brunoni and colleagues [26]. Participants will also be provided with a contact phone number in case they experience side effects/adverse events prior to study staff check-ins or in case questions or other issues arise. Participants will be reminded that if they experience vertigo (a dizzy feeling, similar to the sensation of rocking on a boat) despite the predetermined intensity set during the in-person visit at Butler Hospital, they should decrease the intensity immediately until the dizziness stops.

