The Project Leaders of this supplement, [REDACTED] will be responsible for and supervise data collection and data management. The main goals of this study involve assessing feasibility (i.e., > 75% of CES sessions completed) and acceptability (i.e., < 20% attrition in the sample) of a 4-week course of CES in active-duty firefighters (i.e., at least 16 out of 20 firefighters complete at least 15 out of 20 sessions over four weeks) and obtaining preliminary signal of effect to inform the design of a future, collaborative clinical trial to test efficacy of CES for the prevention of PTSD in first responders. Our primary outcome measures include the number of completed sessions to quantify feasibility and attrition in the sample assessing acceptability (Aim 1). In addition, we will collect data on subjective fatigue, negative and positive emotions using ecological momentary assessment (Aim 2) as well as heart rate variability and sleep quality (Aim 3). Finally, we will collect pre- and post-CES data on clinical symptoms (PTSD, depression, anxiety) and MRI-based resting state functional connectivity and structural connectivity (Aim 3). Given the preliminary nature, the proposed study is not designed to have adequate power to robustly test whether CES is effective for PTSD prevention, which would constitute the long-term goal of the proposed work. As such the proposed number of 20 individuals is solely meant to achieve the listed aims.

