All research personnel will be trained to properly administer the study protocol by the PIs/ Project Leaders Drs. [REDACTED]. This training will specifically focus on administration of clinical measures, CES, and MRI, as well as the ability to train the research participants in the self-administration of CES. Drs. [REDACTED], as the Project Leaders will be responsible for documentation of training through sign off. All research staff will have completed research ethics training; including data management and procedures for maintaining data confidentiality and safety before being allowed to work on the project.

3) Human Subjects

A. Subject Population

Participants will be 20 active-duty firefighters within the State of Rhode Island. The Providence Fire Department is the largest fire department in the State of Rhode Island, employing about 400 firefighters, and is the second largest department in New England. No participant will be requested to change any medical care they might receive to participate in this study. Ongoing medical care will be recorded. In accordance with the NIH guidelines, efforts will be made to obtain a mix of study participants in terms gender, racial, and ethnic representation. Only participants who can give fully informed voluntary written consent will be accepted. Participants will be free to withdraw from the study at any time without penalty. Participants will be at minimum 18 years old and maximum 56 years old. The upper age limit of 56 is based on current practice in Rhode Island that firefighters are not older than 35 years of age when they become a firefighter and that firefighters can retire after 20 years of duty. As such most firefighters will have retired from active duty at age 55. We included a one-year margin to avoid excluding participants who turn 56 during the study.

Study inclusion criteria include:

- (1) active-duty firefighter in the State of Rhode Island;
- (2) age between 18-56 years;
- (3) be in good medical health or, if having chronic medical conditions, these conditions need to be stable;
- (4) ability to speak, read, write, and understand English sufficiently well to complete study procedures and provide informed consent.

Study exclusion criteria include:

- (1) CES-related contraindications, e.g., implanted metallic device or substances including pacemakers, implanted or wearable defibrillators, pregnancy or planning to become pregnant during the study duration;

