- (2) neurological conditions such as brain neoplasm, cerebrovascular events, epilepsy or history of seizures, dementia, and neurodegenerative disorders, or had previously received brain surgery;
- (3) report presence of suicidal ideation on QuickSCID-5 or has attempted suicide one or more times within the past twelve months;
- (4) exhibiting a psychiatric condition that would require inpatient or partial psychiatric hospitalization;
- (5) current moderate or severe alcohol or other substance abuse (excluding nicotine and marijuana);
- (6) major or unstable medical illness requiring further investigation or treatment;
- (7) do not own a smartphone or not able or willing to install EMA and/or Oura ring app on personal smartphone;
- (8) inability to operate the CES device after training and/or intolerance to CES during in office session on Visit Day 1.

If asked to complete MRI scanning, participants will be screened for MRI eligibility criteria, e.g., no cochlear implant, metallic tattoos, undefined metal in the body, claustrophobia, pregnancy. However, not being able to complete MRI is not an exclusion for participation.

B. Recruitment and Consent Procedures

Potential participants will be recruited from fire stations within the greater Providence metro area. Brochures and flyers using IRB approved language will be distributed at fire stations, and through social media advertisements. Potential participants will be able to contact the research team to express interest. In addition, research team members will visit recruitment sites (e.g., fire stations) to increase awareness of the study and potentially interested individuals might provide their name and phone number for a research team member to contact them for further information.

Individuals who inquire about participation will be contacted by study staff by phone call, or text from the designated study cell phone for initial contact. Individuals will be provided with a brief verbal description of the study, and invited to participate if they appear eligible based on pre-screening. At the beginning of Visit 1, participants will meet with study staff in a private room and will be provided with a written explanation of study procedures, risks, and benefits and research staff will carefully explain all aspects of the study, including potential risks and benefits, and the expected duration and time commitment of their participation.

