Participants will be given the opportunity to ask any questions they may have, take as long as they need to decide if they want to participate (e.g., they can take the consent form home to think it over), and if they remain interested, written informed consent will be obtained by a member of the study team who has received training in the protection of human research participants. Participants will receive a copy of the informed consent document including contact information, should any questions or concerns arise at a later time. After informed consent is obtained, participants will be further evaluated to confirm eligibility.

C. Potential Risks

Potential risks to all subjects include:

- (1) Breach of confidentiality or loss of privacy. In the course of this study we will collect sensitive information which, if released, may cause shame, embarrassment, or distress. Additionally, due to the nature of at-home CES, EMA, and Oura ring (if applicable), colleagues, family members, and/or friends might find out about study participation which might be uncomfortable.
- (2) Distress due to assessment procedures: Asking participants about their thoughts, feelings, behaviors, and potential psychiatric symptoms during the clinical interviews, completion of rating scales, and during the EMA surveys might increase distress or result in discomfort.
- (3) Perception of coercion to participate in the study: Participants may feel coerced to participate.
- (4) MRI: The bore of an MRI scanner is narrow, which can cause a claustrophobic reaction in some participants. For the real scanner there is the additional small risk that participants will experience heating

during the scan from exposure to radio frequency (RF) coils. Furthermore, there are risks associated with MRI scanning associated with metal implants near the magnet, including metallic tattoos. Finally, there is the risk of discovery of unknown potential health problems. During the MRI procedures, it is possible that signs of a previously unknown health problem may be discovered (e.g., images that contain possible lesions, tumors, cerebrovascular problems) that may cause distress.

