- (5) CES: CES is considered a low-risk technique that is well tolerated and carries minimal to no side effects. CES devices are FDA cleared as Class II devices. The to-be-used CES device (AlphaStim AID) can be purchased online by individuals from the company website (for US customers a 'doctor's note' is required but this can be arranged online on the company website at time of purchase – in the proposed study, release of the device to participants will be provided by physicians in Butler's Neuromodulation Research Facility, following company purchasing practices). Side effects from CES are mild and self-limiting (<1%). The most common side effects include vertigo, nausea, and headache [16, 25], although skin irritation at electrode sites, ear pain, tingling, pulsing or tingling sensations on ears, and tender ears have also been reported. In a large trial in 115 participants with anxiety disorder and comorbid depression reported no adverse events using the Alpha-Stim CES device we propose to use in the current study and with identical settings [27]. CES is thought to be safe without risk of seizure induction in the absence of neurologic risk factors. CES is contraindicated with implanted pacemakers or implanted or wearable defibrillators and pregnancy as safety of stimulation has not been established during pregnancy. It is advised not to use dangerous machinery or vehicles during treatment, and in some cases following treatment.
- (6) EMA: EMA surveys might be frustrating because they ask the same things multiple times. EMA survey notifications delivered during working hours can cause distraction.
- (7) Oura ring: The Oura ring is made from metal and as with any ring, skin irritations or difficulty removing the ring can occur. The Oura ring contains a battery, and when working with batteries, or devices and/or with machinery that contain batteries while wearing the Oura ring, there is a risk of a short circuit when both the cathode and the anode of another battery touch the ring. This can result in a potentially dangerous shock. The Oura is a radio transmitter and receiver. It's designed not to exceed the emission limits for exposure to radio frequency (RF) energy set by the Federal Communications Commission. Ring EMF frequency has an SAR (Specific Absorption Rate) level of 0.0003 W/kg, compared to an SAR level at or below 1.6 W/k for all cell phones sold in the United States.

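### Does exclusion (8), applied at Visit 1, leave the Aim 1 feasibility and acceptability rates without a usable denominator?

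*Combined protocol and SAP*

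**What the plan says.** Section A (Specific Aims) and C4 (Data Analysis) set two limits for Aim 1: over 75% of sessions completed (feasibility) and attrition under 20% (acceptability). Section A illustrates them as "at least 16 out of 20 firefighters complete, for example, at least 15 out of 20 sessions". C4 makes completed sessions and attrition the primary outcomes. C2 (Study Design) recruits 20 and allows for 20% attrition so as to have data on 16. The Subject Population section says "Participants will be 20 active-duty firefighters within the State of Rhode Island".

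The order of events is clear. Under Recruitment and Consent Procedures, "After informed consent is obtained, participants will be further evaluated to confirm eligibility". Under C3, staff set the intensity with the participant at Visit 1, watch a practice session and "assess tolerability of the individually determined stimulation intensity prior to sending participants home with the Alpha-Stim AID CES device". Exclusion (8), "inability to operate the CES device after training and/or intolerance to CES during in office session on Visit Day 1", is decided there.

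The protocol does not say at which of these steps the 20 are counted or whether a firefighter stopped under exclusion (8) is replaced, and C4 does not ask for a tally of such cases.

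**The concern.** Exclusion (8) differs from the other seven exclusions because it depends on how the firefighter gets on with the intervention itself. Being able to operate and tolerate the device is close to what Aim 1 sets out to measure. A firefighter can consent, receive stimulation, fail to manage or tolerate it, and then be labelled ineligible instead of counted as attrition.

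If the 20 are those who start home use, both Aim 1 rates leave such people out and can only look better than the rates among all otherwise eligible firefighters who consented. The study is meant to inform a later efficacy trial, so a reader would want to know which population the feasibility conclusion describes and how many were stopped at the door. With only 20 people, one or two cases could also move attrition across the 20% limit.

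**Working it through.** **The plan's own figure.** 16 / (1 − 0.20) = 20, so the recruitment figure in C2 reproduces exactly.

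**Two ways to count.** Let *d* be dropouts among starters and *k* the number stopped under exclusion (8). The documents give no value for *k*.

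*20 are starters, removals replaced.* Attrition is d/20 among starters and (d + k)/(20 + k) among all consented and otherwise eligible.

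| d | k = 0 | k = 1 | k = 2 | smallest k reaching 20% |
|---|---|---|---|---|
| 3 | 3/20 = 15.0% | 4/21 = 19.0% | 5/22 = 22.7% | 2 |
| 2 | 2/20 = 10.0% | 3/21 = 14.3% | 4/22 = 18.2% | 3 (5/23 = 21.7%) |
| 1 | 1/20 = 5.0% | 2/21 = 9.5% | 3/22 = 13.6% | 4 (5/24 = 20.8%) |
| 0 | 0% | 1/21 = 4.8% | 2/22 = 9.1% | 5 (5/25 = 20.0%) |

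*20 are consented, no replacement.* With k = 2 and 15 completers, attrition is 3/18 = 16.7% of starters and 5/20 = 25.0% of consented. The denominator can therefore matter in principle.

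**Sessions.** Scoring removals as zero sessions multiplies the starter rate by 20/(20 + k), which is 0.952 for k = 1 and 0.909 for k = 2. The starter rate would have to be no higher than 0.75 × 21/20 = 78.75% (k = 1) or 0.75 × 22/20 = 82.5% (k = 2) for the 75% limit to be missed.

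**How likely removals are.** Section C (Potential Risks) puts side effects below 1% and cites a trial in 115 participants that "reported no adverse events using the Alpha-Stim CES device we propose to use in the current study and with identical settings". Taking adverse events as a rough stand-in for intolerance (an assumption), the exact one-sided 95% upper bound for 0/115 is 1 − 0.05^(1/115) = 2.6%. Neither figure measures inability to operate the device, so 5% is added as a stress value; it has no source in the documents.

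With failure rate *p* and recruitment until 20 start, P(k ≥ 1) = 1 − (1 − p)^20 and P(k ≥ 2) = 1 − (1 − p)^20 (1 + 20p).

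**How often the verdict differs.** Take *d* as binomial (20, *q*) with q = 0.05, 0.10, 0.15 and 0.20, independent of *k*, and *k* as negative binomial. Under the strict limit, sum the probability that d/20 < 0.20 while (d + k)/(20 + k) ≥ 0.20. The worked example of 16 out of 20 is exactly 20% attrition, so the sum was repeated with exactly 20% passing: d/20 ≤ 0.20 while (d + k)/(20 + k) > 0.20.

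| p | P(k ≥ 1) | P(k ≥ 2) | verdict differs, strict <20% | verdict differs, 20% passes |
|---|---|---|---|---|
| 1% | 18% | 2% | 0.1–0.5% | 0.4–4% |
| 2.6% | 41% | 10% | 1–3% | 2–11% |
| 5% (stress) | 64% | 28% | 5–9% | 5–21% |

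The last column is larger because 4 dropouts among 20 starters then pass, and a single removal gives 16/21 = 76% completing, which is 24% attrition.

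**The case for a change.** The strongest argument for a change is that nothing in the protocol states the screen-failure reading outright. The recruitment wording in C2 could mean 20 consented, and the text uses the word participants for people whose eligibility is not yet confirmed. The weekly review in D3 covers enrolment, adverse events and attrition, and D3 also tracks noncompliance and withdrawal. That is monitoring for risk, though, and does not name exclusion (8) cases or tie them to Aim 1. A sentence in C4 would cost almost nothing and would stop the denominator being chosen after the results are known.

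The factual part of this stands: the sentence is absent. The harm does not follow from it. That the rates describe only people who passed the office check holds only if the 20 are starters. In that case the rates answer a proper question, namely how a four-week home course goes among people cleared to begin it, and a later trial with the same check would need that figure. The design also works against removals: the intensity is lowered until dizziness stops, staff guide the set-up, and inability counts only after training. People who struggle or stop at home remain in both rates.

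A second set of rates with Visit 1 failures scored as zero sessions answers a different question, and whether to show it is a matter of preference. The numbers consented, stopped and started let any reader work out attrition on the wider base.

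**Conclusion.** No change to the plan is needed. The protocol leaves unstated at which step the 20 are counted, and an analyst would fill that gap sensibly by treating exclusion (8) as a screen failure, reporting the Aim 1 rates among those who began home CES, and giving the flow from consent to start. Either reading of the 20 yields a sound result for the population it names.

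The size is unknown and probably small. At failure rates of 1% to 2.6%, the strict attrition verdict would differ in about 0.1% to 3% of studies, or about 0.4% to 11% if exactly 20% attrition passes. Only the unsourced 5% rate gives more. These figures assume that adverse events stand in for intolerance, that removals are replaced until 20 start, that starter dropout is 5% to 20%, and that dropout is independent of Visit 1 failure. They do not cover inability to operate the device, for which the documents give no rate.

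What is at stake is clarity about whom the conclusion describes, in a single-arm pilot that C4 says is not powered to test effectiveness. That can be settled when results are written up, without altering what the trial does or what it can conclude.
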